8.2.3.3 Collecting Fasting Blood Sample and Urine for Storage

Fasting blood sample and spot urine sample will be collected in all patients on Day 1 and Week 24 (or at EOT/EW for patients who discontinue the study), frozen, and archived for potential evaluation of safety biomarkers as needed for additional study analyses. These

samples will be collected and stored in accordance with all national and local regulations, and after the patient has completed the informed consent process. If no analysis of the sample is performed, it will be destroyed when safety assessments required for regulatory submission of this study are complete. No genetic testing will be performed on these samples.

8.2.4 Vital Signs

Vital signs (pulse rate, respiration rate, temperature, and BP) will be measured as per the schedule in [Appendix A](#).

An automatic sphygmomanometer will be dispensed to sites. For BP, the patient will have 3 measurements taken on the nondominant arm while seated (see [Appendix G](#)). Prior to the first measurement, the patient should remain seated at rest for at least 5 minutes. Following the 5-minute rest period, 3 separate seated BPs should be measured with at least 1 minute between BP measurements and with the cuff fully deflated between measurements. The value for analysis and entry criteria (Screening) will be the mean of these 3 measurements. It is recommended that BPs be assessed by the same person, if feasible, using the same calibrated equipment, on the same arm. Additional measurements may be obtained if clinically indicated.

Three seated pulse rate measurements will be obtained. The mean of the 3 seated pulse rate measurements will constitute the pulse rate value for that visit.

Note: Vital sign measurements should be measured after the patient has been seated for at least 5 minutes and prior to phlebotomy.

8.2.5 Physical Examinations, Height, and Weight

Complete physical examinations will be performed at Screening, and Week 24 (or EOT). A complete physical examination will include, at minimum, a review of the patient's general appearance, head, eyes, ears, nose and throat, neck, heart, lungs, abdomen, back and extremities, skin, and general neurological system.

A symptom-related brief physical exam will only occur if the patient is experiencing symptoms or AEs. If a symptom-related brief physical exam is required, it should include a review of all body systems that relate to the symptoms and/or AE the patient is experiencing.

Height (without shoes) will be measured once, during Screening.

Weight will be measured at Screening and at all other clinic visits. The patient should be weighed at approximately the same time of day, wearing minimal clothing (ie, no coat/shoes), and using the same calibrated scale at each visit, where possible. BMI will be calculated.

8.2.6 Electrocardiograms

The 12-lead ECG will be performed as per the schedule in [Appendix A](#). The 12-lead ECG recordings should be conducted prior to the morning study drug administration. ECGs should be recorded either prior to phlebotomy or at least 30 minutes after phlebotomy.

All ECGs will be sent to a central ECG vendor for evaluation. Details on processing will be provided to the sites in a separate ECG manual.

8.2.7 Demographics

The following variables will be recorded on the appropriate eCRF: age, sex, and race/ethnicity (as permitted by local regulations).

8.2.8 Medical History

A general medical history will be collected at the Screening Visit and Week -2. The eCRF will include specific questions about relevant exclusion criteria, for example, a history of DKA.

8.2.9 Other Assessments

Other assessments will be completed as per the schedule [Appendix A](#) and include: informed consent, medication history, FSH for females who are postmenopausal, and TSH (at Screening only; if abnormal, free thyroxine will be measured).

8.3 Study Procedures and Assessments by Visit

Study procedures and assessments are presented by visit in [Appendix A](#) and [Appendix I](#).

8.3.1 General Guidelines

The timing of the visits and follow-up telephone contacts for this trial are given relative to the day of randomization. The patients should be encouraged to return for their visits as close to the scheduled visit date as possible. Patients should be encouraged to fast (with the exception of water or noncaffeinated, zero-calorie beverages) for at least 8 hours before collection of any fasting laboratory samples. If the patient is unable to fast as above, the scheduled “fasting” laboratory samples will still be collected and the non-fasting status will be noted in the eCRF and on the laboratory requisition form. ALL data collected will be used in the evaluations, including data that may originate outside the investigative site, such as non-visit (unscheduled) clinical laboratory evaluations.

Any events that occur between scheduled visits should be recorded by the Investigator as soon as they come to his or her attention.

Note: If serum creatinine increases by $\geq 30\%$ above the Baseline value during the study, then the Investigator should consider assessment of: volume status, diuretic dosage, discontinuing NSAIDs, and other relevant testing including renal imaging techniques, as appropriate.

Sodium-glucose cotransporter type 2 inhibitors are associated with osmotic diuresis and volume depletion, which may lead to dizziness or hypotension, especially in the elderly. All patients will be advised to maintain proper fluid intake and to consider increasing it if they sense greater thirst, more urine production, or if they feel dizzy or faint. Investigators should consider closer monitoring of renal function in patients assessed to be at risk for deterioration of renal function. This may include evaluation of relevant laboratory tests at an unscheduled visit a week after initiating double-blind study drug.

Visits should be scheduled in the morning, at approximately the same time of day.

Prior to each visit, patients should be contacted and reminded of the date and time of their appointment.

In addition, the patient should be instructed to:

1. Bring the study drug bottles (used and unused) to the clinic. **Note:** Patients should not take study drug on the day of the visit until instructed by site staff. Patients should be instructed to take their basal insulin on the day of the visit, but not to take bolus insulin on the day of the visit until instructed by site staff.
2. Bring glucose meter and study diary to the clinic visit

Study assessments will be done according to the following detailed visit schedule presented in the subsequent sections.

At each visit, patients will be asked if to their knowledge any EOSI has occurred since the last visit.

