- f. Vital sign measurements should be measured after the patient has been seated for at least 5 minutes and prior to phlebotomy.
- g. The 12-lead ECG recordings should be obtained prior to the morning study drug administration. ECG recording should be recorded either prior to phlebotomy or at least 30 minutes after phlebotomy.
- h. The patient will be provided with a study diary and glucose monitoring supplies for use at home. These supplies will be provided to all sites by the Sponsor.
- i. After the initial dispensation at the Screening Visit, additional Ketostix[®] (or similar) will be dispensed on an as needed basis.
- j. Counseling frequency may be increased at the discretion of the Investigator.
- k. Concomitant medications taken from 2 weeks prior to the Screening Visit through the EOT, including those specified in the inclusion/exclusion criteria, must be recorded in the source documents.
- l. All SAEs will be collected starting with signing informed consent/assent and continue until 30 days after the last dose of study drug.
- m. The collection of AEs will start after the first dose of double-blind study drug. All AEs ongoing at the EOT/EW visit should be followed for at least 30 days following the last dose of study drug or until the event has resolved, the condition has stabilized, the etiology of the event is determined to be not related to study drug, or the patient is lost to follow-up.
- n. Patients participating in the satiety substudy will be instructed to complete their satiety daily diaries before the first meal of the day. The patients will be instructed to complete the diaries each day during the 14day, ± 3 days single-blind placebo Run-in Period and each day for the last 14 days, ± 3 days of the double-blind Treatment Period (during Week 23 and Week 24).
- o. Entries on the satiety daily diaries should be reviewed and recorded on the eCRF.
- p. Fasting blood samples should be taken after the patient has fasted for at least 8 hours; patients should only drink water or noncaffeinated, zero-calorie beverages. If the patient is unable to fast as above, the scheduled "fasting" laboratory samples will still be collected, and the non-fasting status will be noted in the eCRF.

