5 DATA HANDLING

5.1 Time Points and Visit Windows

Day 1, defined as the Baseline/Randomization visit, is also the first day that study treatment is planned to be started. Should study treatment start at a later date, Day 1 will be defined as the date that study treatment is initiated. Relative days after Day 1 are calculated as (assessment date – Day 1 date) + 1. Relative days prior to Day 1 are calculated as (assessment date – Day 1 date). The day prior to Day 1 is Day -1; there is no Day 0.

The following visit windows defined in [Table 5.1-1](#) will be used for the by-visit analyses of the primary endpoint, the secondary and other endpoints. All other analyses will use the nominal study visit as defined in the Study Schedule and eCRF.

In general, the Baseline value for a variable is defined as the last value collected or taken on or before Day 1, prior to the first dose of double-blind study drug. In cases where there are multiple such values, the non-missing value closest to the start of study treatment is selected. If time is available for an assessment on Day 1, it will be compared with dosing time on Day 1 to define the Baseline value.

If there are multiple visits (scheduled or unscheduled) within a visit window, the measurement closest to the target day of the visit will be used in the analysis. If the measurements are equally distant to the target day, then the later one will be used in the analysis. An exception to these rules applies to the variable hypoglycemic events per patient per day by SMBG, where a scheduled visit takes precedence over an unscheduled visit. Hypoglycemic events by SMBG are based on the data entered in a patient's study diary, and hence, it is more appropriate to choose the scheduled visit when a patient would typically return the diary to the site over an unscheduled visit.

Statistical Analysis Plan

Version: Final 1.0

Lexicon Pharmaceuticals Protocol No. LX 4211.1-312-T1DM

Date of Issue: 17 MAR 2017

Covance Study ID: 000000145143

Table 5.1-1 Definition of Visit Windows

| Visit | Target Day of Visit ^a | A1C, Insulin, Hypoglycemic Events per Day by SMBG, Body Weight, Vital Signs, FPG, Serum Chemistry, Beta-hydroxy Butyrate (BHB) | Urinalysis, Urine Albumin, Urine Calcium, Urine Glucose, Urine Creatinine, PSDD-NRS ^b | Fasting Lipid Profile, Hematology |
|--------------------------------|----------------------------------|--|--|-----------------------------------|
| 1 Baseline ^c | 1 | ≤1 | ≤1 | ≤1 |

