6.8.4 Other Efficacy Analysis

Analysis of other efficacy endpoints will be based on the mITT population, with the exception of the 2 endpoints based on the PSDD-NRS, which will be based on the Satiety substudy population. Descriptive statistics for these efficacy endpoints will be presented by treatment group and by study visit where appropriate. All post-Baseline data will be used in the analyses, including observations occurring after discontinuation of study drug.

For continuous efficacy endpoints, MMRM or ANCOVA model will be used as specified in [Section 6.8](#). The choice in statistical models depends on whether the measurement process is over multiple timepoints (MMRM) or at a single timepoint (ANCOVA).

For binary efficacy endpoints, CMH test and 95% CLs based on normal approximation methods with a continuity correction factor will be used, as described in [Section 6.8](#).

Figures displaying mean change from Baseline by visit, LS mean change, and bar charts displaying proportions, will be presented by treatment groups for selected parameters, as appropriate.

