6.8.4.7 Change from Baseline in FPG

Descriptive statistics of FPG (mg/dL) will be presented by treatment group and visit. Change from Baseline in FPG at Week 24 and other visits will be analyzed using MMRM statistics with change from Baseline as the endpoint and Baseline FPG-by-time interaction as a covariate. Treatment effects at Week 24 and other visits will be presented.

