6.9.8 Laboratory Evaluations

Data for the following hematology, serum chemistry, lipid profile, and urinalysis analytes received from the central laboratory will be listed and summarized by treatment group and visit (Table 6.9-1). If data for any additional analytes are also received then these will be listed only.

Statistical Analysis Plan

Version: Final 1.0

Lexicon Pharmaceuticals Protocol No. LX 4211.1-312-T1DM

Date of Issue: 17 MAR 2017

Covance Study ID: 000000145143

Table 6.9-1 Central Laboratory Assessments

| Hematology | Serum Chemistry | Lipid Profile | Urinalysis |
|--|--|---|--|
| Complete blood count (CBC) Differential Platelet count Hemoglobin Hematocrit | Sodium Potassium Chloride Carbon dioxide (bicarbonate) BUN Creatinine Glucose (serum) ALT AST Total bilirubin Alkaline phosphatase (ALP) Uric acid Calcium Phosphorus Total protein Albumin Magnesium Creatine phosphokinase (CPK) Lactate dehydrogenase (LDH) | Total cholesterol Triglycerides HDL-C LDL-C Non-HDL-C | Urine albumin Urine calcium Urine glucose Urine creatinine Urine pregnancy test Urine dipstick with microscopy: Specific gravity pH Protein Blood Ketones Bilirubin Urobilinogen Nitrate Leukocyte esterase |
| Other Blood Samples | | | |
| A1C FPG Serum pregnancy test - females only Follicle-stimulating hormone (FSH) - if necessary to confirm postmenopausal status BHB Anion gap Thyroid stimulating hormone (TSH) | | | |

All summaries of laboratory test results will be presented in International System of Units (SI) and conventional units. Out-of-reference-range values will be flagged as high (H) or low (L) in the listings.

For analysis purposes, values preceded by a “<” or a “>” sign (ie those below or above the limits of quantification) will be considered equal to the lower or upper limit of quantification, respectively.

Laboratory evaluations measured on a continuous scale will be summarized by visit using standard descriptive statistics for the Safety population. Changes from Baseline will also be summarized. For analysis by visit, analysis windowing as described in [Section 5.1](#) will be utilized for each scheduled visit such that unscheduled visit will also be considered. For each laboratory analyte, the Baseline value will be defined as last scheduled or unscheduled value collected prior to the first dose of treatment.

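### Samples flagged non-fasting enter the FPG model and the lipid summaries, which mixes post-meal values into analyses labelled fasting

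*Protocol*

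**What the plan says.** Protocol Appendix A, note p, sets the standard: "Fasting blood samples should be taken after the patient has fasted for at least 8 hours". Protocol 8.3.1 covers the patient who arrives without having fasted. The scheduled samples are drawn all the same, and "the non-fasting status will be noted in the eCRF and on the laboratory requisition form". The sentence directly after that says "ALL data collected will be used in the evaluations", and it extends this to unscheduled laboratory results. Note p and the visit lists in Appendix I repeat the instruction to draw and flag.

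FPG is one of the 'other' efficacy endpoints (Protocol 10.3.1.3, SAP 3.1.3). For that class SAP 6.8.4 says "All post-Baseline data will be used in the analyses, including observations occurring after discontinuation of study drug". For FPG itself, SAP 6.8.4.7 says "Change from Baseline in FPG at Week 24 and other visits will be analyzed using MMRM statistics", with Baseline FPG-by-time as covariate. Where several results fall in one visit window, SAP 5.1 says "the measurement closest to the target day of the visit will be used in the analysis".

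The fasting lipid profile is handled as safety laboratory data under SAP 6.9.8: "Laboratory evaluations measured on a continuous scale will be summarized by visit using standard descriptive statistics for the Safety population". Protocol Table 8.2.3-1 has LDL-C calculated by the Friedewald equation, not measured.

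Neither document uses the recorded flag to exclude, adjust, stratify or define a sensitivity analysis. SAP Section 7 lists no change on the point.

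**The concern.** The trial records which samples are non-fasting and then makes no analytic use of that record. A glucose value taken after a meal is not an FPG value, and it does not carry the same treatment effect. Protocol 3.1.1 attributes to the drug a delay and reduction of intestinal glucose absorption, with lower post-meal peaks. It also reports a 50 to 60 mg/dL reduction in post-meal glucose from Baseline in a one-week study of type 2 patients with renal impairment. An FPG comparison containing flagged values therefore estimates a blend of a fasting and a postprandial effect while being labelled as the former.

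The visit instructions could enlarge the gap. Under Protocol 8.3.1 patients take basal insulin on visit days but hold bolus insulin until told otherwise, so a patient who has eaten may have done so without mealtime insulin.

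The same mislabelling affects lipids: non-fasting triglycerides would be summarized as fasting values, and any distortion carries into calculated LDL-C. The protocol itself treats fasting as material here, since exclusion criterion 3b requires fasting status to be verified when a patient fails on triglycerides.

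What is at stake is the meaning of one 'other' efficacy endpoint and some descriptive safety tables.

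**Working it through.** The plan states no figure to reproduce. The check is a trace of one flagged sample through the text, followed by an illustration on assumed inputs.

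**Trace of a flagged glucose sample**

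1. It is drawn and flagged (Protocol 8.3.1; Appendix A, note p).
2. It is retained under the all-data sentence in Protocol 8.3.1 and the all-post-Baseline rule in SAP 6.8.4.
3. It can be the value chosen for its window, because SAP 5.1 selects on distance from the target day only.
4. It enters the FPG MMRM (SAP 6.8.4.7), which has no fasting condition or covariate.
5. A flagged Day 1 value before dosing becomes Baseline under SAP 5.1. It then enters both the change score and the covariate. Because it precedes dosing, randomization balances it on average, so it adds error without favoring an arm.

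A flagged lipid sample follows steps 1 to 3 (the all-post-Baseline rule in SAP 6.8.4 aside) and then reaches the SAP 6.9.8 summaries.

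**Effect on the treatment difference**

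Let f be the non-fasting share at a visit, equal in both arms. Let E_F be the treatment reduction in fasting glucose and E_N the reduction in non-fasting glucose.

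- Expected difference = (1 − f) × E_F + f × E_N
- Shift from the fasting effect = f × (E_N − E_F)

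The documents give neither f nor E_N − E_F. Both are assumed: f from 2% to 20%, and E_N − E_F from 10 to 50 mg/dL.

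| f | E_N − E_F = 10 | 30 | 50 |
|---|---|---|---|
| 2% | 0.2 | 0.6 | 1.0 |
| 5% | 0.5 | 1.5 | 2.5 |
| 10% | 1.0 | 3.0 | 5.0 |
| 20% | 2.0 | 6.0 | 10.0 |

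Entries are in mg/dL.

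**Effect on precision**

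Assume a fasting SD of 70 mg/dL, a non-fasting SD of 80 mg/dL, and non-fasting values higher by a shift D of 40 or 80 mg/dL, in a simple single-visit comparison.

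- Keeping flagged samples: variance = 4900(1 − f) + 6400f + f(1 − f)D², and SE ratio = √(variance / 4900).
- Dropping them: SE ratio = 1/√(1 − f).

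| f | D (mg/dL) | Variance if kept | SE ratio, keep | SE ratio, drop |
|---|---|---|---|---|
| 5% | 40 | 4655 + 320 + 76 = 5051 | 1.015 | 1.026 |
| 5% | 80 | 4655 + 320 + 304 = 5279 | 1.038 | 1.026 |
| 20% | 40 | 3920 + 1280 + 256 = 5456 | 1.055 | 1.118 |
| 20% | 80 | 3920 + 1280 + 1024 = 6224 | 1.127 | 1.118 |

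Dropping is worse at a 40 mg/dL shift and about one percentage point better at 80 mg/dL. The planned MMRM adjusts for Baseline and borrows from other visits, so these ratios are only indicative, but they show that precision is not a reason to exclude.

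**The case against.** The all-data sentence is a general rule about data sources in a section on visit procedures, and it names neither FPG nor lipids. The SAP 6.8.4 rule is aimed at data after drug discontinuation, and the table shells are in a separate file that could not be checked. On this view the plan is merely silent. That stands only in part. The sentence follows the non-fasting instruction directly, the SAP repeats an all-data rule for this endpoint class, and nothing gives the flag a role. A programmer following the text would include the flagged values.

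A reader might infer that the flagged values make the FPG estimate materially noisier and that excluding them would tighten it. The SE comparison does not support this.

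A reader might also infer bias from unequal non-fasting rates, for instance if treatment of hypoglycemia or ketosis with carbohydrate differs by arm. Taking 5% to 20% in one arm and half that in the other, with shifts of 40 to 80 mg/dL, gives 0.025 × 40 = 1 to 0.10 × 80 = 8 mg/dL. But nothing in the documents indicates such an imbalance. The trial is double-blind, and the fasting reminder in Appendix I is the same for everyone.

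The strongest objection concerns exclusion itself. After Day 1, fasting status is a post-randomization condition that may depend on glycemia, so setting flagged values to missing leans on the MAR assumption of SAP 5.2.2. This stands, and it is why the all-samples analysis should be kept alongside.

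**Conclusion.** The point holds as one of validity. Under the plan as written, flagged non-fasting values are analyzed as FPG and summarized as fasting lipids. On the assumed ranges, the FPG difference would shift by 0.2 to 10 mg/dL, and by 1.5 mg/dL in a middle case (f = 5%, effect gap 30 mg/dL). The shift would favor the drug only if its effect after a meal exceeds its fasting effect. The documents make that plausible but do not quantify it for this population. If non-fasting samples are rare, the effect is negligible.

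The consequence is limited. FPG is outside the testing sequence in Protocol 10.4.1 and SAP 6.8, and lipids are descriptive safety data. A reader might infer that A1C results are also compromised, because note p is attached to A1C in the schedule. The argument here concerns meal effects on glucose and lipids and gives no ground for extending it to A1C. The primary endpoint, the four secondary endpoints, alpha and the sample size are untouched. This is a low-cost improvement, not a defect in the trial's main conclusions.

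**What to change.** In SAP 6.8.4.7 and 6.9.8, state that the FPG and lipid analyses use only values not flagged non-fasting. Set flagged values to missing before the SAP 5.1 window selection, so that an unflagged sample in the same window can be chosen.

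- **Baseline:** no new rule is needed. SAP 5.1 already takes the non-missing pre-dose value closest to the start of treatment.
- **Sensitivity analysis:** keep the analysis on all samples, flagged ones included.
- **Reporting:** give non-fasting rates by arm and visit.
- **Scope:** limit the rule to FPG and lipids, and say that A1C is unchanged.

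The work is a few lines of SAP text, a filter on a flag already in the eCRF, one repeat of the FPG and lipid outputs, and one small table.

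The costs are real but modest. Some FPG and lipid observations are lost, which may slightly widen the confidence interval. FPG and lipids are not scheduled at Week -2 (Appendix A), so a flagged Day 1 value sends Baseline back to Screening, before the run-in and any insulin or medication changes made then. If the Screening value is flagged too and no other pre-dose value exists, the patient has no FPG Baseline. Exclusion also relies on MAR given a status observed after randomization. Comparing the two analyses and reading the rates by arm will show whether that matters.
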